13.11 Analysis of Exploratory Genomic Endpoints

Mutations in DDR genes can be seen in around 30% of patients with metastatic CRPC.³⁴ We hypothesize that presence of these mutations would sensitize tumor cells to the DNA damaging effects of radium-223 and result in a longer PFS. The study is planned to enroll 45 patients who will receive radium-223. Assuming 10% will not have adequate tissue for sampling, we estimate that we will have adequate samples from at least 40 patients available for the correlative study. Using a log-rank test with a one-sided type I error of 0.15, there is 80% statistical power to detect an improvement in median PFS from 6 months (patients without DNA repair mutation) to 12 months (patients with a DNA repair pathway mutation) corresponding to hazard ratio of 0.50 (Table 21).

Table	21:
-------	-----

Assumptions:							
• N=40 (ev	• N=40 (evaluable samples)						
Median I	PFS in non-mutated DNA repair grou	up = 6 mor	ths				
DDR	Targeted median PFS (mos)	ШD	N (PFS	D			
mutation prevalence	in patients with patients with DDR mutation	HR	event)	Power			
		0.5	26	0.8			
0.3	12	0.5	36	0.0			
0.3	13	0.46	36	0.85			
0.4	12	0.5	36	0.82			
0.4	13	0.46	35	0.87			

The distributions of PFS and OS will each be summarized using the product-limit method of Kaplan-Meier according to prevalence of baseline genomic alternations (e.g., with or without DNA repair mutation). Median times for each endpoint will be presented with two-

sided 95% CI estimated using log(-log(survival)) methodology. Log-rank test will be used to compare the median PFSs between the DDR mutation groups. Kaplan-Meier estimates of the endpoints at 6 or 12 months after treatment initiation may also be presented with two-sided 95% confidence intervals.

For the cfDNA analysis, patients will be dichotomized based on baseline tumor purity status into 2 groups: high (tumor purity >7.5%) vs. low (tumor purity \leq 7.5%). The cutoff choice was based on the prior study that demonstrated 7.5% to be the lower limit of accurate detection for tumor derived cf-DNA.⁵⁷ Kaplan-Meier estimates will be used to assess the distribution of PFS according to tumor purity status. Medians of time to PFS will be shown with two-sided 95% CIs.

An exploratory landmark analysis will be performed and will include all patients who have not progressed (no PFS event) by 13 weeks and have available cf-DNA at baseline and week 13. Change in tumor purity from baseline to week 13 on therapy would be used as a binary variable (increase/stable tumor purity vs. decreased tumor purity) to assess its impact on subsequent PFS. The 13 week time point was chosen to allow for the first restaging scans (12 weeks) after initiation of therapy and allow for sufficient exposure to pembrolizumab considering prior studies in melanoma and NSCLC have demonstrated a median time to response of around 8-12 weeks.^{58,59} Cox regression model will be employed to assess the association of PFS and change in tumor purity, with estimated hazard ratio (increase/stable tumor purity vs. decreased tumor purity) and corresponding 95% CI.

The proportion of patients with PSA response ($\geq 50\%$ decline from baseline) will be presented with a two-sided 95% CI using exact binominal method according to baseline genomic alternation (e.g., DDR mutations). Change in PSA will also be summarized descriptively according to the genomic alteration groups and the changes in PSA will also be compared between genomic alteration groups using the Wilcoxon rank sum tests

Other secondary objectives will be summarized descriptively.

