 - Correlation of DNA damage repair (DDR) mutations in baseline tumor samples and circulating cf-DNA with progression-free survival (PFS) on radium-223 ± pembrolizumab.
 - DDR encompasses genes such as BRCA1, BRCA2, FANCA, ATM, PALB2, HDAC2 and CK2
 - PFS will be defined as time from randomization to:
 - Appearance of 2 or more new bony lesions compared to baseline, confirmed on a repeat bone scan ≥6 weeks later
 - Appearance of new soft tissue lesions on CT/MRI or progression of existing ones per RECIST 1.1 criteria
 - Death from any cause
 - Prevalence of mutations in DDR genes in tissue or cf-DNA in patients with metastatic CRPC treated with Ra-223
 - Incidence of novel genomic alterations detected at the time of progression as mechanisms of treatment resistance
 - Impact of baseline cf-DNA tumor purity (defined as percentage of tumor derived circulating DNA; high: >7.5% vs. low: \leq 7.5%) on subsequent PFS
 - Change in tumor purity from baseline to weeks 5 and 13
 - Impact of change in tumor purity at 13 weeks (increased/stable vs. decreased compared to baseline) on PFS
 - PSA response (defined as PSA decline ≥50% compared to baseline) and overall survival (OS: defined as time from randomization to death from any cause) in patients with and without DNA repair mutations on radium-223 ± pembrolizumab.

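### The DDR log-rank test pools both arms without stratifying by treatment, so a chance DDR-by-arm imbalance combined with a strong arm effect could distort this trial's DDR result

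*Combined protocol and SAP*

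**What the plan says.** Section 13.11 plans a comparison of PFS by DDR status. Its premise on prevalence is: "Mutations in DDR genes can be seen in around 30% of patients with metastatic CRPC". The sample size starts from an expected loss: "Assuming 10% will not have adequate tissue for sampling". Out of 45 enrolled, the section then concludes: "we estimate that we will have adequate samples from at least 40 patients available for the correlative study". The test level is given as "Using a log-rank test with a one-sided type I error of 0.15". The power claim for the comparison is: "there is 80% statistical power to detect an improvement in median PFS from 6 months"; the target for mutated patients is 12 months, a hazard ratio of 0.50. The analysis sentence is: "Log-rank test will be used to compare the median PFSs between the DDR mutation groups".

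Section 13.1 lists the endpoint as the correlation of DDR mutations "in baseline tumor samples and circulating cf-DNA with progression-free survival (PFS) on radium-223" with or without pembrolizumab, so both arms enter one comparison. Section 13.11 mentions neither stratification by arm nor arm as a covariate. Section 13.3 names two randomization strata, alkaline phosphatase and volume of bone metastases; DDR status is not one of them. By contrast, Section 13.9 allows for adjustment by treatment arm in the quality-of-life models.

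**The concern.** The stated hypothesis is that DDR mutations sensitize tumors to radium-223. The arms differ in pembrolizumab and also in radium-223 timing: under Sections 5.1 and 5.4, Arm A has a planned break after three doses if disease is at least stable, while Arm B has none. Whether the combination changes PFS is a secondary question of the trial, so a null arm effect cannot be taken for granted.

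With about 12 mutated patients and no design balance, their split between arms is left to chance. If they cluster in the arm with longer PFS, an arm effect can look like a DDR effect. If they cluster in the other arm, it can mask one. The trial is run once and the split will be visible. Deciding to adjust only after seeing it would be post hoc.

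**Working it through.** **Inputs.** From Section 13.11: 40 evaluable patients (45 × 0.9 = 40.5), prevalence 0.30 (12 mutated, 28 not), DDR hazard ratio 0.50, one-sided 0.15, 36 PFS events. The first row of Table 21 is garbled in the text available; 36 is the count that reproduces its power. From Section 1.1: 2:1 allocation, so about 27 of 40 in Arm A and 13 in Arm B. Assumed, because the documents give no value: arm hazard ratio (A against B) from 0.5 to 1.0, the same in both DDR groups.

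**Step 1: the plan's power.** Schoenfeld: power = Φ(√(d·p(1−p))·|ln HR| − z₀.₈₅).
√(36 × 0.3 × 0.7) = √7.56 = 2.750. Then 2.750 × 0.693 − 1.036 = 0.869, and Φ(0.869) = 80.8%, against 80% stated. The figure reproduces.

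**Step 2: how likely is an imbalance?** Let k be the number of the 12 mutated patients in Arm A, hypergeometric with 27 of 40 in Arm A.
- P(k ≥ 11) = 3.3%
- P(k ≥ 10) = 15%
- P(k ≤ 6) = 12%
- P(7 ≤ k ≤ 9) = 20.5% + 28.4% + 24.0% = 73%

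**Step 3: how far does it shift the comparison?** Approximately, the DDR log hazard ratio moves in favor of the mutated group by −ln(HR_arm) × [k/12 − (27 − k)/28].
- k = 11: 0.917 − 0.571 = 0.345. At arm HR 0.5 the shift is 0.693 × 0.345 = 0.239, and the false-positive rate is Φ(2.750 × 0.239 − 1.036) = 35%. At arm HR 0.7 it is 24%.
- k = 6: 0.500 − 0.750 = −0.250. At arm HR 0.5 the effective log hazard ratio is 0.693 − 0.173 = 0.520, and power is Φ(2.750 × 0.520 − 1.036) = 65%. At arm HR 0.7 it is 73%.

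**Step 4: simulation.** Exponential PFS; in the main runs, censoring uniform at 18–36 months. Events are not fixed at 36. With arm HR 0.5 and a true DDR effect there are about 31, so power is lower than in Step 3.

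| Condition | Arm HR | Unstratified | Stratified |
|---|---|---|---|
| False positives, k = 11 | 0.5 | about 31% | about 15% |
| | 0.7 | about 22% | about 15% |
| | 0.8 | about 19% | about 15% |
| | 1.0 | about 14% | about 15% |
| Power, k = 6 | 0.5 | about 55% | about 70% |
| | 0.6 | about 63% | about 72% |
| | 0.7 | about 67% | about 72% |

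At k = 10 and arm HR 0.5 the unstratified false-positive rate is 23%. At the most likely split, k = 8, it is 13% against 14% stratified.

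**Step 5: average over randomization.** Unstratified type I error is about 13–15% over the assumed range. Mean power, unstratified against stratified:
- arm HR 1.0: 78% and 76%
- arm HR 0.7: 75% and 74%
- arm HR 0.6: 73% and 73%
- arm HR 0.5: 70% and 71%

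**Step 6: follow-up.** Section 13.2 plans 6 months after accrual and about 2 years in total. With 6–24 months of follow-up instead, the k = 11 false-positive rate at arm HR 0.5 is 30%, and power at k = 6 is 48% against 62%. Absolute power falls, but the contrast is similar.

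**The case against.** The strongest case against is that nothing is wrong with the test on average. Arm is randomized independently of baseline DDR status, so the unstratified log-rank test keeps its nominal level and stratifying barely changes mean power. That stands. A reader might infer from the conditional figures that the planned test has an inflated type I error, or that any pembrolizumab effect would double it. The documents support neither. Doubling needs an arm HR of about 0.5, which appears nowhere in the plan, together with a split of about 3% probability. At arm HR 0.8 the rate is about 19% even at that split. The most likely splits (7 to 9 of 12) carry 73% of the probability and do far less. The false-positive and power harms also need opposite imbalances, so one trial cannot suffer both.

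A second objection is that stratifying does not isolate sensitivity to radium-223. That also stands. Section 9.5 itself links impaired DNA repair to checkpoint-blockade response. If pembrolizumab helped only mutated patients (HR 0.5) and DDR status had no effect on radium-223 outcome, then with 8 of 12 mutated patients in Arm A the stratified test would still reject 57% of the time, against 59% unstratified. The plan frames the question as radium-223 with or without pembrolizumab, so pooling is a choice and not an oversight.

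Third, the analysis is exploratory, at one-sided 0.15, and no decision rule depends on it. That limits severity. What survives is that a valid average error rate is little help in reading a single result in which, say, 10 or 11 of 12 mutated patients received the combination.

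**Conclusion.** The point holds as a minor one. The DDR comparison is unstratified, the arms receive different regimens, and DDR status is not balanced by design. A chance imbalance combined with a strong arm effect could therefore distort the result of this one trial. In the unfavorable cases examined, at arm HR 0.5, the conditional false-positive rate is about 31% instead of 15%, or conditional power is about 55% instead of 70%; the imbalances behind them have probabilities of about 3% and 12%. At arm HR 0.7 the figures are about 22%, and 67% against 72%.

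These are conditional figures. They rest on 12 mutated patients among 40, 27 in Arm A, exponential PFS, an assumed arm HR, and no DDR-by-arm interaction. They do not show that the plan's error rate or its stated 80% power is wrong; the power figure reproduces.

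**What to change.** In Section 13.11, specify a log-rank test stratified by treatment arm at the same one-sided 0.15, and report an arm-stratified Cox hazard ratio with its confidence interval. In the same line, describe the test as comparing PFS distributions, since a log-rank test does not compare medians.

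The cost is one line of text and about 1–3 points of power if there is no arm effect. State that stratification guards against chance imbalance only and does not separate a DDR-by-pembrolizumab interaction from radium-223 sensitivity. Kaplan-Meier curves by DDR status within arm could be shown descriptively, but with about 12 × 13/40 = 3.9 mutated patients expected in Arm B they will not settle that question.

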13.12 Reporting and Exclusions

13.12.1 Evaluation of Toxicity

All participants will be evaluable for toxicity from the time of their first treatment.

13.12.2 Evaluation of the Primary Efficacy Endpoint

There is no primary efficacy endpoint.

Analyses of secondary efficacy endpoints will be on an intent-to-treat basis. Specifically, all eligible participants included in the study must be assessed for response/outcome to therapy, even if there are major protocol therapy deviations.

Subanalyses may then be performed on the basis of a subset of participants,

excluding those for whom major protocol deviations have been identified (e.g., early death due to other reasons, early discontinuation of treatment, major protocol violations, etc.). However, these subanalyses may not serve as the basis for drawing conclusions concerning treatment efficacy, and the reasons for excluding participants from the analysis should be clearly reported. If applicable to the endpoint, the 95% confidence intervals will be provided.

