1. OBJECTIVES

1.1 Study Design

This is a randomized phase II open label study of pembrolizumab, a humanized monoclonal antibody (mAb) of the IgG4/kappa isotype designed to directly block the interaction between PD-1 and its ligands PD-L1 and PD-L2, in combination with radium-223. A total of 45 patients with advanced metastatic CRPC will be randomized in a 2:1 fashion to the combination of pembrolizumab plus radium-223 (Arm A) or to radium-223 alone (Arm B).

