1.3 Secondary Objective

- To assess the safety and tolerability of combination therapy with pembrolizumab plus radium-223
- To preliminarily investigate the efficacy of the combination of pembrolizumab plus radium-223 as evaluated by progression-free survival (PFS) and overall survival (OS)

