9.1.1 Bone biopsies

The bone biopsies will be core needle or excisional biopsies. These biopsies will be performed per standardized clinical guidelines at Brigham and Women's Hospital and at the corresponding department for participating investigational sites. Tissue will be embedded into paraffin. Sites that have been previously irradiated are not permitted. The second biopsy should be done at the same site as the original biopsy when possible. If the first biopsy is non-diagnostic, a second pre-treatment biopsy should be performed if safe and acceptable to the patient and treating physician. The patient will not be eligible to enroll if no tumor tissue can be identified by the pathology team (touch prep evaluation will suffice). If the patient is enrolled and it is later determined that the first biopsy is not diagnostic or useful towards assessing the primary endpoint of increase in T cell infiltrate, then they will not be required to undergo the on-treatment biopsy. If the patient

is already on study treatment, they may continue on the study therapy even if no ontreatment biopsy is obtained.

The on-treatment biopsy should be done after at least 2 doses of radium-223 unless the second dose of radium-223 cannot be given due to safety/toxicity. If the latter, it should follow the protocol dictated time window (week 8 or within 3 weeks after week 8). If it cannot be performed for safety reasons or patient refusal (as long as patient initially agreed), it will not be considered a deviation.

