11.1.3 Methods for Evaluation of Disease

Imaging studies will be reviewed by independent radiologists at the Tumor Imaging Metrics Core at DFCI. Ultimately, all scans will undergo central review at DFCI for final response analysis. However, for eligibility and ongoing response assessment while on study therapy, UCSF review will be per investigator assessment.

All measurements should be taken and recorded in metric notation using a ruler, calipers, or a digital measurement tool. All baseline evaluations should be performed as closely as possible to the beginning of treatment and not more than 42 days before the beginning of the treatment.

The same method of assessment and the same technique should be used to characterize each identified and reported lesion at baseline and during follow-up. Imaging-based evaluation is preferred to evaluation by clinical examination unless the lesion(s) being followed cannot be imaged but are assessable by clinical exam.

Conventional CT and MRI. This guideline has defined measurability of lesions on CT scan based on the assumption that CT thickness is 5mm or less. If CT scans have slice thickness greater than 5 mm, the minimum size of a measurable lesion should be twice the slice thickness. MRI is also acceptable in certain situations (*e.g.* for body scans).

Use of MRI remains a complex issue. MRI has excellent contrast, spatial, and temporal resolution; however, there are many image acquisition variables involved in MRI, which greatly impact image quality, lesion conspicuity, and measurement. Furthermore, the availability of MRI is variable globally. As with CT, if an MRI is performed, the technical specifications of the scanning sequences used should be optimized for the evaluation of the type and site of disease. Furthermore, as with CT, the modality used at follow-up should be the same as was used at baseline and the lesions should be measured/assessed on the same pulse sequence. It is beyond the scope of the RECIST guidelines to prescribe specific MRI pulse sequence parameters for all scanners, body parts, and diseases. Ideally, the same type of scanner should be used and the image acquisition protocol should be followed as closely as possible to prior scans. Body scans should be performed with breath-hold scanning techniques, if possible.

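### Section 13.12.2 labels the PFS and OS analysis intent-to-treat but defines its set as eligible participants, so the wording permits dropping a randomized patient later judged ineligible (minor)

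*Combined protocol and SAP*

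**What the plan says.** Section 1.1 fixes the design: "A total of 45 patients with advanced metastatic CRPC will be randomized in a 2:1 fashion", open label, which gives 30 and 15 patients. Section 1.3 names PFS and OS as the secondary efficacy endpoints.

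Section 13.12.2 gives their analysis set in two steps. First the label: "Analyses of secondary efficacy endpoints will be on an intent-to-treat basis". Then the definition: "Specifically, all eligible participants included in the study must be assessed for response/outcome to therapy, even if there are major protocol therapy deviations". It also allows optional subanalyses "excluding those for whom major protocol deviations have been identified", and says these may not be the basis for conclusions about efficacy.

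Section 13.6 gives a different set for the same endpoints. Its primary analysis population is dosed patients with biopsy assessments at baseline and 8 weeks, and it is assigned to primary, secondary and exploratory endpoints. It does not mention eligibility.

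On the biopsy as an eligibility condition, Section 9.1.1 says "The patient will not be eligible to enroll if no tumor tissue can be identified by the pathology team". It also anticipates a different case: "If the patient is enrolled and it is later determined that the first biopsy is not diagnostic or useful towards assessing the primary endpoint". That patient is excused the on-treatment biopsy and may stay on therapy. Section 3.2 requires proof of tumor, but lets a patient enroll on a good-faith basis after a second non-diagnostic biopsy.

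On imaging, Section 11.1.3 sends all scans to central review at DFCI for the final response analysis, but "for eligibility and ongoing response assessment while on study therapy, UCSF review will be per investigator assessment".

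**The concern.** Intention to treat means every randomized patient, analysed in the assigned arm. A set defined by eligibility equals that set only if nobody's eligibility is reopened after randomization. If it is reopened, the decision comes when the arm is known and outcomes may be accumulating. It would probably turn on features related to prognosis, such as soft-tissue disease or tumor content of the lesion. Randomization would then no longer protect the PFS and OS estimates, although the report would still carry the intention-to-treat label.

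**Working it through.** The documents give no sample size, event count or power for comparing PFS or OS between arms, so there is no stated figure to reproduce. The nearest count, 36 evaluable of 45 in Section 13.4 (45 × 0.80 = 36), allows for inadequate specimens and loss to follow-up. It says nothing about ineligibility. The main check is therefore on the text.

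**Text**

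1. The word *Specifically* makes the second sentence of 13.12.2 the definition of the first. The defined set is eligible participants.
2. The retention clause covers therapy deviations. Enrollment in breach of an entry criterion is not a therapy deviation, so the clause does not reach it.
3. No other section keeps such a patient in the PFS and OS analysis. By contrast, 13.12.1 makes all participants evaluable for toxicity, with no eligibility condition.
4. Ineligibility is not an off-study criterion in 5.6, and 5.5 continues follow-up whatever the reason for stopping treatment. Survival data on such a patient should therefore exist. PFS data may be thinner, because 5.5 does not require follow-up scans after treatment in patients who have not progressed.
5. No sentence orders removal, and none defines eligibility for analysis purposes.

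**Size, under assumptions**

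Let k be the number judged ineligible after randomization. The documents give no value; k from 0 to 6 is assumed.

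- Patients analysed: 45 − k. For k = 1, 5 and 6 this is 44, 40 and 39, so 2.2%, 11.1% and 13.3% are removed.
- Share of an arm per exclusion: 1/15 = 6.7%; 1/30 = 3.3%.
- Approximate standard-error ratio, √(45/(45 − k)): 1.023 for k = 2 and 1.074 for k = 6.
- Shift in a progression-free proportion (assumed outcomes, no censoring):

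| Arm | All randomized | Drop 1 (event / no event) | Drop 2 (events / no events) |
|---|---|---|---|
| 15 patients | 8/15 = 53.3% | 8/14 = 57.1% / 7/14 = 50.0% | 8/13 = 61.5% / 6/13 = 46.2% |
| 30 patients | 15/30 = 50.0% | 15/29 = 51.7% / 14/29 = 48.3% | 15/28 = 53.6% / 13/28 = 46.4% |

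- Shift in the overall median PFS: solve (k/45)·2^(−t/m) + (1 − k/45)·2^(−t/6) = 0.5, where m is the median of the excluded patients and 6 months that of the rest. With m assumed between 3 and 12 months, the all-randomized median is 5.81 to 6.16 months for k = 2 and 5.44 to 6.51 for k = 6, against 6.0 in the eligible-only set. The 6 months is borrowed from 13.11, where it is the assumed median without a DNA-repair mutation. It is a placeholder, not a forecast for this trial.

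**The case against.** The best defence is that the sentence is written to keep patients in, and that eligible participants included in the study may simply mean those who passed the eligibility check at registration. Section 4.1 has an investigator confirm eligibility then, and no later eligibility ruling is described. This reading is available and may be what was meant. The text does not secure it, however, because nothing says that eligibility is fixed at registration for the purpose of analysis.

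The defence does defeat several stronger readings that a reader might infer:

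- **That patients will in fact drop out.** No sentence says so; exclusion is only an implication of one word.
- **That central review at DFCI will overturn eligibility at UCSF.** Section 11.1.3 makes the investigator's reading the one that counts for eligibility there, and gives central review a role in the final response analysis only.
- **That a baseline biopsy later found non-diagnostic makes the patient ineligible.** Section 9.1.1 attaches no such ruling; the stated consequence is that the second biopsy is not required. Section 3.2 allows good-faith enrollment after two non-diagnostic biopsies, which sits badly with the eligibility sentence in 9.1.1. Whether such a patient is eligible is unclear, and the two sections need to be reconciled.
- **That the 20% allowance measures the problem.** It covers specimens and loss to follow-up.
- **That a type I error rate is affected.** Section 13.8 plans Kaplan-Meier summaries of PFS and OS by arm, with no test between arms.

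**Conclusion.** The point stands as a mismatch between label and definition. As worded, the set in 13.12.2 is not intention to treat, because it permits removing a randomized, treated patient on a later eligibility finding. The severity is minor. The effect is confined to descriptive PFS and OS estimates, is probably small, and is zero if nobody is reclassified. If it occurs it will show most in the 15-patient arm, where one exclusion removes 6.7% of patients and, in the illustration, moves the proportion by 3 to 4 percentage points. All of these sizes rest on assumed counts and outcomes; the documents support no estimate of how many patients would be affected.

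**What to change.** Two edits are needed together.

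1. In 13.12.2, replace the definition with: *PFS and OS analyses include all randomized participants in the arm to which they were randomized, regardless of any later finding on eligibility. An analysis restricted to eligible participants may be reported as a labelled sensitivity analysis.*
2. In 13.6, limit the paired-biopsy population to the biopsy endpoints and refer PFS and OS to the set in 13.12.2. Otherwise 13.6 would still restrict PFS and OS to dosed patients with both biopsies, planned at 36 of 45, and the first edit would have no effect.

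While these are open, reconcile 3.2 with 9.1.1 on the status of a patient with a non-diagnostic baseline biopsy. Also check the all-randomized wording against 4.1, which cancels the registration of a patient who receives no protocol therapy.

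The cost is a few sentences and no new visits. Survival follow-up is already required by 5.5. Where scans stop after treatment, the existing rule of censoring at the last disease evaluation applies.
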